The DUS will identify a minimum of 600 patients newly initiating RPV-containing regimens and 600 patients newly initiating EFV-containing regimens and captured in one or more of the HIV cohorts currently established in Europe. Exposure to RPV-containing regimens will be measured by the presence of prescription records for the fixed dose combination (FDC) of RPV with emtricitabine/tenofovir (TRUVADA TM (Gilead)) or single agent tablets of RPV among the patient data. Exposure to EFV will be measured by the prescription records for the available formulations of EFV in patient data. Information on drug use, including dispensing date, dose prescribed, quantity dispensed and the length of drug supply, will also be captured from the prescription records in the cohort database. The sample size targets will produce an error rate of no more than 5% for the proportions estimated. A minimum of 600 RPV-treated patients will be included in the DUS to assess the proportion of appropriate use of RPV-containing regimens. The study period will start at the date of market availability of RPV-containing products in the participating counties and will end when in total 600 patients from each treatment group have been included in the study and followed for 12 months, until virologic failure, or lost to follow-up, whichever occurs first.

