Several large HIV cohort databases have investigated the prevalence of transmitted drug resistance (TDR). Among 525 chronically infected treatment-naïve patients in the EuroSIDA cohort, the overall prevalence of TDR was 11.4% from 1996-2004 (Bannister, 2008). In the German HIV-1 Seroconverter cohort of 1276 patients, the overall prevalence of TDR was 12.4% from 1997 through 2007. NRTI associated resistance was identified most frequently (6.3%), followed by NNRTI resistance (2.4%) and PI resistance (2.1%) (Bartmeyer, 2010). In the Swiss HIV cohort of 822 newly infected patients identified from 1996-2005, the overall prevalence of TDR was 7.7% for any ARV drug, 5.5% for NRTIs, 1.9% for NNRTIs, and 2.7% for PIs (Yerly, 2007). A recent investigation by the UK Collaborative Group in HIV drug resistance reported a decline in the rate of TDR in treatment-naïve recently and chronically infected patients from around 14% in 2001-2002 to around 8% by the end of 2004 (Dunn, 2007).

The level of adherence to antiretroviral therapy (ART) is one of the critical factors in achieving viral suppression, avoiding viral rebound, increasing CD4 cell counts, and minimizing the risk of development of AIDS-defined illnesses that may result in death among HIV-infected patients on ART (Cambiano, 2010). Patient self-reports via questionnaires or interviews is the most frequently used measure of treatment adherence to HAART. More quantitative measures exists, such as electronic monitoring devices, pill counts, and pharmacy prescription refill monitoring; however use of these methods is limited by high cost, labor intensity, and other issues (Nieuwkerk and Oort, 2005). Self-report questionnaires that have been used in the clinical setting and validated include the simplified medication adherence questionnaire (SMAQ), the visual analog scale (VAS), the Adult AIDS Clinical Trials Group (AACTG) questionnaire, and the Self-Reported Adherence (SERAD) (Deschamps, 2008). While self-reports offer significant correlation

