In summary, a DUS (using data from multiple existing HIV cohorts in Europe) will be conducted in order to address the CHMP concerns on the potential for development of virologic resistance and potential for improper prescribing or use (according to the SmPC). HIV cohorts have a demonstrated history of assessing virologic failure, RAMs, and associated risk factors. This DUS will provide significant real-world data on (amongst other parameters) ARV drug resistance, frequency of resistance testing, viral load at the start of treatment, prior use of ARV treatment, reasons for switch of ARV treatment, adverse events, concomitant medications and comorbidities. Currently, the HIV cohorts do not routinely collect data on ARV pill adherence or pill intake with food. The feasibility of collecting data on ARV treatment adherence and pill intake with food within the HIV cohorts for each patient at each visit will be assessed. Additionally, a nested case-control study will be conducted to assess the effects of ARV treatment adherence and pill intake with food on the risk of virologic failure with RPV will be assessed. As the nested case-control analysis will assess a smaller sample of RPV-treated patients that have already been identified as part of the DUS, details on the study design are included in this protocol.

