Exposure to RPV will be determined by the presence of prescription records for the FDC of FTC/RPV/TDF or single agent of RPV among patient data. Relevant drug codes will be used to identify RPV-containing regimens in the HIV cohorts. The baseline date for exposure follow-up (index date) for a patient within a given treatment group will be defined by first prescription of RPV or EFV-containing regimens. Duration of exposure will be based on dispense date and days of supply for each dispensed prescription. Exposure to RPV or EFV-containing regimens will be considered discontinued if the prescription is not refilled within a specified interval of time (e.g. twice the days' supply) of the previous prescription. Switches from one drug to another will be captured and time on drug will be defined by the exposure periods. The total length of exposure to a given drug will be the time between start and stop periods of exposure to the same drug.

4.2.1.1. **Exposure Definition in Nested Case-Control Study**

For the nested case-control analysis, exposure will be based on 1) level of daily medication adherence, and 2) level of adherence to food recommendations. Cases and matched controls that are selected will be asked to retrospectively report via a questionnaire how often they took their HIV medication during a specified time period and how often RPV was taken with food. A single item querying the number of prescribed doses the participant had missed in a specified time period will be used, as follows:

"How many doses of your complete HIV regimen did you miss in the last 7 days?"

"For those days you missed, what component of your HIV regimen did you miss?" (If applicable)

"How often did you take RPV with food in the last 7 days?"

Since RPV dosing is once-daily, number of doses taken is equivalent to number of days the medication is taken. A 7-day recall period is proposed for this analysis as it has the advantage of including a weekend, during which adherence is often problematic. Further, DATE (6 September 2011) 20

longer recall periods (7-day vs. 1-3 day) may yield more useful data for once-daily ART dosing since there are too few dosing times in a very brief recall period to capture variations in adherence behaviors (Simoni, 2006).

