5. STUDY LIMITATIONS

The proposed study is based on analysis of medical and prescription records from databases maintained by HIV cohorts in Europe. The following limitations should be considered:

There is potential misclassification of the diagnosis or the outcomes of interest.

Attribution of loss of virologic control to failure to follow RPV-containing products' SmPC may not be feasible given the multiple factors and dynamics salient to virologic control

Measurement of adherence to treatment regimens are difficult to assess with reliability beyond prescription refills. Reasons for switch of ARV treatment may be captured inconsistently across the HIV cohorts. Adverse events during the course of RPV or EFV-treatment will be described in aggregate; it is not possible or appropriate to assess the causality of individual cases.

Daily measurement of patient food intake with RPV-containing regimens is highly problematic in any study given the time required to measure diet consistently and accurately over the course of the study period. Associations between patient diet measurement and loss of virologic control are likely highly unreliable given misclassification of diet and consistent measurement of dietary intake. Furthermore, a thorough measurement using complicated instruments of the patient's dietary intake may result in changes in dietary behavior to an extent that the behavior becomes unrepresentative of true intake in the 'real world' setting.

Self-report of treatment adherence is susceptible to recall bias and social desirability bias. Self-reported measures reflect only short-term or average adherence and may often overestimate it, particularly when queried retrospectively.

DUS include bias related to the observational nature of the data and potential lack of data due to loss to follow-up or essential data not collected as routine fields. These studies are also subject to real-world prescribing practices that may not provide sufficient patient numbers to meet study goals of ascertainment within a reasonable timeframe. The feasibility evaluation and design assessment of the study are intended to better understand and adjust for these limitations as well as to estimate the probability to meet study goals of ascertainment within a reasonable timeframe.

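### ARV adherence is fixed as a one-time seven-day self-report taken after failure; the dispensing records the study already captures are never used as a second adherence measure dated before failure

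*Protocol*

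**What the plan says.** For the nested case-control study, Section 4.2.1.1 defines ARV adherence by questionnaire: "Cases and matched controls that are selected will be asked to retrospectively report via a questionnaire how often they took their HIV medication". The Synopsis describes it as a single contact covering the past seven days. Patients count as adherent above 80%, and Sections 4.3.3 and 4.5.4 build the odds ratio on that split. Quantifying the risk of failure associated with adherence is the stated primary objective of this analysis (Section 1.3.1).

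On dispensing data, the Synopsis says: "Information on drug use, including dispensing date, dose prescribed, quantity dispensed and the length of drug supply, will also be captured from the prescription records". Section 4.2.1 puts them to use: "Duration of exposure will be based on dispense date and days of supply for each dispensed prescription". The same section ends exposure when a refill gap exceeds a set interval, with double the supply period as its example. Section 4.5.2 reports duration of use and persistence for both drugs, and Section 4.5.3 divides events by person-exposure time. No section turns these records into an adherence percentage.

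On the quality of the measures, Section 5 states: "Measurement of adherence to treatment regimens are difficult to assess with reliability beyond prescription refills". It adds that self-report is open to recall and social desirability bias and may overestimate adherence, particularly when asked retrospectively. Section 1.1 likewise says that self-report misses nonadherence.

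**The concern.** Cases enter the nested study because they have already failed. They, and their controls, are then asked about the last seven days, counted back from the questionnaire. Three weaknesses follow. The window may fall after the failure it is meant to explain. A patient who knows that treatment has failed may answer differently from one whose treatment is working. And one week is a short sample of behaviour over a follow-up of up to 12 months.

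Dispensing records are dated, are made without reference to the outcome, and can be cut off before failure. If they are left out of the adherence analysis, the only estimate of the effect of ARV adherence rests on the measure whose bias the protocol itself describes, with nothing to check it against. At stake is the credibility of the adherence odds ratio. The appropriate-use proportions and the RPV versus EFV failure rates are not affected.

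**Working it through.** **1. Coarseness of the questionnaire scale.** Seven once-daily doses give adherence of (7 − k)/7: 100%, 85.7%, 71.4% and so on. The >80% rule therefore means at most one missed dose in one week.

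**2. Whether dispensing records could separate patients at 80%.** Under the example rule in Section 4.2.1, a patient given 30 days' supply who refills every 60 days is still continuously exposed, at 30/60 = 50% coverage. Variation on both sides of 80% therefore remains among patients counted as on treatment.

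**3. The protocol's power figures.** Inputs from Section 4.1.2: two-sided alpha 0.05, 4:1 controls, 50% exposed (p0 = 0.5). With p1 = OR·p0/(1 + (OR − 1)·p0), d = p1 − p0, r controls per case and p̄ = (p1 + r·p0)/(1 + r):

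power = Φ{[d√n − 1.96·√(p̄(1 − p̄)(1 + 1/r))] / √(p1(1 − p1) + p0(1 − p0)/r)}

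- OR 3.0, n = 40: p1 = 0.75, p̄ = 0.55. (1.581 − 1.090)/0.500 = 0.982, power 0.837 (Table 1: 0.828).
- OR 2.0, n = 90: p1 = 0.667, p̄ = 0.533. (1.581 − 1.093)/0.534 = 0.914, power 0.820 (Table 1: 0.816).

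Table 1 reproduces and is not in error.

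**4. What sampling costs.** Information relative to unlimited controls is r/(r + 1). For 4:1 sampling this is 0.80. For all 600 RPV patients it is (600 − n)/600. The share kept is therefore 480/(600 − n).

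| Cases | Share kept | OR | Power, 4:1 | Power, all 600 |
|---|---|---|---|---|
| 20 | 480/580 = 0.83 | 3.0 | 0.522 | 0.608 |
| 40 | 480/560 = 0.86 | 3.0 | 0.837 | 0.895 |
| 40 | 480/560 = 0.86 | 2.0 | 0.471 | 0.533 |
| 90 | 480/510 = 0.94 | 2.0 | 0.820 | 0.843 |

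The loss from sampling is modest.

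**5. What misclassification could cost.** Exposure here is nonadherence, 50% among controls. Sensitivity (se) and specificity (sp) of self-report are assumptions, because the protocol gives none against true adherence. The 88% and 79% in Section 1.1 are measured against virologic failure. The observed proportion is se·p + (1 − sp)(1 − p). For se 0.9, sp 0.95 and OR 3.0:

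- cases: 0.9 × 0.75 + 0.05 × 0.25 = 0.6875
- controls: 0.9 × 0.5 + 0.05 × 0.5 = 0.475
- observed OR: (0.6875/0.3125)/(0.475/0.525) = 2.43

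| se (sp 0.95) | True OR 3.0 seen as | Power, 40 cases | True OR 2.0 seen as | Power, 90 cases |
|---|---|---|---|---|
| 1 (sp 1) | 3.00 | 0.837 | 2.00 | 0.820 |
| 0.9 | 2.43 | 0.68 | 1.78 | 0.68 |
| 0.7 | 1.94 | 0.46 | 1.56 | 0.47 |
| 0.5 | 1.67 | 0.29 | 1.42 | 0.30 |

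This assumes equal error in cases and controls. If the error differs between them, the bias can run in either direction. Refill adherence has errors of its own, which the documents do not quantify, so the table shows what is at risk with self-report and not what refills would recover.

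**The case against.** The protocol did consider the alternatives. Section 1.1 lists refill monitoring among the quantitative methods and says: "pharmacy prescription refill monitoring; however use of these methods is limited by high cost, labor intensity, and other issues". It also notes that self-report is the most used method and correlates with viral load, and that no method exists for comparing adherence across the many cohorts. Section 2.2 excepts robust adherence measures from what the cohorts hold, and Section 1.1 says: "Currently, the HIV cohorts do not routinely collect data on ARV pill adherence or pill intake with food". The nested study was built mainly for the food question, which refills cannot answer, and it is coherent to take both exposures from the same patients over the same week. The Synopsis also plans, if feasible, to collect adherence at each visit for all RPV patients and add it to the main analysis.

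Much of this stands. A reader might infer from Section 5 that the protocol endorses refills as the reliable measure. That sentence only states a limit, and Section 1.1 supports self-report in part. A reader might also assume refill data are in hand for all 1,200 patients. The cohorts are still to be chosen (Section 3.1.3.1), and some may lack dispensing records. An RPV versus EFV comparison of adherence is not a listed objective, so its absence breaks no commitment.

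Three parts do not stand. The cost objection has little force for records that the study will capture anyway. The per-visit plan is conditional, limited to RPV and not refill-based, and Section 4 gives it no analysis. Nor can the matter be left to an unseen analysis plan, because Section 4.2.1.1 fixes the exposure measure and Section 4.5.4 builds the model on it.

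**Conclusion.** The point holds as a missed second measure. The study captures dated supply records for both drugs and uses them for duration, discontinuation, persistence and person-time, but not for adherence. The only adherence exposure fixed in Section 4 is a single seven-day self-report taken after failure.

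Two stronger readings are not supported. The first is that studying a matched subsample throws away much of the power. With 600 RPV patients and 20 to 90 cases, 4:1 sampling keeps about 83% to 94% of the information. Larger power losses would require an assumed questionnaire response rate, for which the documents give no basis. The second is that refills should replace self-report as the main exposure. Given Sections 1.1 and 2.2, that is a debatable trade-off.

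The size of the bias is unknown. Under the assumed error rates, a true odds ratio of 3.0 could appear as 2.43 to 1.67, and power with 40 cases could fall from 0.84 to between 0.68 and 0.29. The change is worth making because it is cheap and gives an adherence measure that precedes failure and does not depend on recall.

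**What to change.** - **Section 4.2.1:** define refill adherence as days supplied divided by days elapsed, over a fixed, pre-stated window that ends before the failure date, or before the matched index date for controls.
- **Section 4.5.4:** add it to the conditional logistic analysis as a pre-specified second ARV-adherence exposure beside the questionnaire measure.
- **Section 4.5.3:** add it as a time-updated covariate in a Poisson model for virologic failure in all RPV patients, and describe refill adherence in EFV patients for context.
- **Coverage:** restrict these analyses to cohorts that record dispensing data, and report how many patients that covers.
- **Questionnaire:** keep it for food intake and self-reported adherence.

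The cost is analysis work, with no new patient contact. The downside is that supply is not ingestion, and cohorts without dispensing records cannot contribute, so the refill result may represent only part of the study population.

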4.2.2. Outcome Definition and Measures

Outcome definitions for the DUS will include:

- HIV viral load prior to initiating RPV-containing regimens or EFV-containing regimens as well as over the course of therapy
- Virologic failure defined for treatment naïve patient as plasma HIV-1 RNA levels >500 copies/ml after 6 months of regimen initiation if baseline viral load is >500 copies/ml. For patients undetectable at baseline virologic failure is defined as 2 consecutive plasma HIV-1 RNA levels >500 copies/ml after starting the regimen.
- HIV treatment status (naïve/experienced) at RPV or EFV treatment initiation
- Prior use of ARV treatment, if any
- NNRTI drug resistance at RPV or EFV treatment initiation as well as over the course of therapy
- Proportion of patients who have resistance testing prior to initiating RPV or EFV therapy as well as over the course of therapy

- Concomitant medications prior to initiating RPV or EFV therapy as well as over the course of therapy
- Comorbidities prior to initiating RPV or EFV therapy as well as over the course of therapy
- Reason for discontinuation of RPV or EFV-containing products
- Reason for switch of ARV treatment
- Adverse events over the course of RPV or EFV therapy

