Virological response to highly active antiretroviral therapy (HAART) regimens has been evaluated among patients enrolled in large, observational HIV cohorts. These studies have included evaluations of NNRTI and protease inhibitor (PI)-containing regimens (Paredes, 2000; Cozzi-Lepri, 2002) as well as short term and long term virological response when treated with NNRTI or PI-based HAART regimens (Mocroft, 2006). A few cohort studies have specifically examined virological failure among patients initiating nevirapine (NVP)-containing regimens or EFV-containing regimens. Phillips and colleagues conducted a study among 2203 patients in EuroSIDA who began a regimen with nevirapine or efavirenz after July 1997 (Phillips, 2001). A total of 1325 patients initiated NVP and 878 EFV. During a median of 8 months follow-up, 669 patients experienced virological failure giving an overall rate of 0.48 per year (0.83 per year if excluding those in first 6 months of follow-up who had baseline viral load >500

copies/ml). A total of 505 people on a NVP regimen experienced virological failure compared with 164 people on an EFV regimen, giving incidence rates of 0.55 per personyear and 0.35, respectively. A more recent EuroSIDA analysis examined virological outcome and drug resistance in 759 patients starting NNRTI-containing regimens (Bannister, 2008). A total of 287 (78.3%) of the 389 NVP patients and 168 (45.4%) of the 370 EFV patients experienced virological failure. NNRTI-resistant HIV was detected in 3% of patients at baseline. Out of the 131 patients still on an NNRTI and with resistance test results available at time of virological failure, NNRTI resistance was detected in 86% of patients and was similar between groups. The high levels of NNRTI resistance suggest that these drugs fostered selection pressure, and that patients had actually adhered to their regimens.

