will be assigned a propensity score ranging from 0 to 1 that represents the fitted probability of receiving RPV-containing regimens. The scores from EFV-treated patients will be plotted against those for RPV-treated patients. Overlap in the treatment groups based on sample size estimates of approximately 600 patients per treatment group in the propensity space must exist for a comparison of outcomes of interest between the two groups.

Incidence rates of virologic failure, pre-treatment resistance, and treatment-emergent resistance will be calculated for the RPV and EFV-exposed patients. The three primary event rates of interest (incidence rates of virologic failure, pre-treatment resistance, and treatment-emergent resistance) will be analyzed in 3 separate sets of analyses. Additional descriptive analyses will include incidence rates for each drug calculated by dividing the number of events by the total person-exposure time and expressed as the number of events per person-year, and 95% confidence intervals. Analyses of virologic failure will be stratified by HIV treatment status (naïve/experienced) at treatment initiation.

Relative risks comparing the RPV-containing regimens with EFV-containing regimens and 95% confidence intervals will be calculated and appropriate stratified analyses will be conducted for virologic failure and emergence of treatment resistance. Poisson regression models will be used to adjust for the appropriate factors that influence the risk of virologic failure and treatment-emergent resistance. Adjustments for imbalances between the treatment groups before receiving the first dose of RPV or EFV-containing regimens will be applied using accepted methods based on sample size availability and the observed overlap of key patient characteristics based on propensity score construction.

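### Some enrolled patients have no virologic failure rule, and failure rates are divided by person-time in which failure cannot be recorded

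*Protocol*

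**What the plan says.** Section 4.2.2 gives two failure rules. One, for treatment-naive patients, reads "plasma HIV-1 RNA levels >500 copies/ml after 6 months of regimen initiation if baseline viral load is >500 copies/ml". The other reads "For patients undetectable at baseline virologic failure is defined as 2 consecutive plasma HIV-1 RNA levels >500 copies/ml after starting the regimen". No further rule is given.

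Section 4.5.3, like the Synopsis, plans "incidence rates for each drug calculated by dividing the number of events by the total person-exposure time". Section 4.2.1 starts exposure at the first prescription, and section 4.2.5 follows each patient for 12 months or until death, loss to follow-up or failure.

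Section 3.1.2 applies no exclusion criteria, and section 2.1 makes all RPV initiators eligible, with EFV initiators eligible by start date. Section 4.5.3 requires the failure analyses to be stratified by naive or experienced status. Describing virologic failure is a primary objective (section 1.3.1), and section 4.2.3 carries the same failure definition into the nested case-control study.

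**The concern.** There are two separate faults.

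- **Missing rule.** A treatment-experienced patient who starts with more than 500 copies, and any patient who is detectable but at or below 500, fits neither definition. Such patients add to the denominators of the rates and of the 12-month proportions, but cannot add an event. Part of the required experienced stratum is thus counted as non-failing by construction.
- **Time not at risk.** A naive patient with baseline above 500 cannot fail before month 6, yet those six months enter the denominator. A patient undetectable at baseline is at risk from the start. The two kinds of patient are pooled in one rate with different shares of usable time.

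At stake are the absolute failure rates, which section 4.5.3 calls primary event rates, the experienced-stratum results and, under conditions set out below, the RPV:EFV relative risk.

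**Working it through.** **Inputs.** From the protocol: the two rules (4.2.2), the start of exposure (4.2.1), 12 months of follow-up (4.2.5) and the cited cohort's figures (1.1). The hazard h per year, the baseline mixes and the stopping rates are assumptions, because the protocol gives none.

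**1. Who has a rule (section 4.2.2)**

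| Baseline viral load | Naive | Experienced |
|---|---|---|
| Above 500 | Above 500 after month 6 | None |
| Detectable, at or below 500 | None | None |
| Undetectable | Two consecutive above 500, from start | Same |

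**2. The protocol's own background figures.** Section 1.1 quotes a cohort rate both ways: "0.48 per year (0.83 per year if excluding those in first 6 months of follow-up who had baseline viral load" above 500.
- Person-years by drug: 505/0.55 = 918 and 164/0.35 = 469, total 1387. Then 669/1387 = 0.48, which reproduces the quoted rate.
- Ratio of the two rates: 0.83/0.48 = 1.73.
- Holding events at 669: 669/0.48 = 1394 and 669/0.83 = 806 person-years. So 1 − 806/1394 = 42% of the time was not at risk.

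**3. Baseline above 500 in this study.** Constant hazard h after month 6, no other exits.
- Events per patient: 1 − exp(−h/2). Time per patient: 0.5 + [1 − exp(−h/2)]/h.
- For h = 0.20: 0.0952/0.9758 = 0.098.
- For h = 0.10, 0.35 and 0.50: 0.049, 0.167 and 0.235.
- The reported rate is 47% to 49% of the hazard after month 6.

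**4. Experienced stratum.** A share x has no rule; the rest are undetectable at baseline with hazard h from the start.
- Rate = (1 − x)[1 − exp(−h)] / {(1 − x)[1 − exp(−h)]/h + x}.
- With h = 0.20 and x = 10%, 25%, 50%: 0.178, 0.146, 0.095.
- The 12-month proportion is multiplied by (1 − x). With x = 25%, 0.1813 reads 0.75 × 0.1813 = 0.136.

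**5. RPV:EFV rate ratio with equal true hazards and no adjustment.** A share f is naive with baseline above 500; the rest are undetectable; h = 0.20 in both. Per patient, events and time are 0.0952 and 0.9758 for baseline above 500, and 0.1813 and 0.9063 for undetectable.
- f = 50%: 0.1382/0.9411 = 0.1469.
- f = 70%: 0.1210/0.9550 = 0.1267.
- f = 90%: 0.1038/0.9689 = 0.1071.
- 50% v 90%: 0.1469/0.1071 = 1.37. 70% v 90%: 0.1267/0.1071 = 1.18.
- Same mix in both groups: 1.00. Within either baseline category: 1.00.
- Other assumed mixes, same h: 50% v 80% naive above 500, with 10% lacking a rule in both groups, gives 1.30. With 70% naive above 500 in both groups, 20% v 5% lacking a rule gives 0.75.
- Different stopping alone (0.1 v 0.2 to 0.4 per year, all with baseline above 500): 1.03 to 1.08.
- On at-risk time every one of these ratios is 1.00.

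**The case against.** The strongest reply is that the comparison is not planned as a crude ratio. Section 4.5.3 checks propensity-score overlap, then uses Poisson adjustment and stratified analyses. The 1.37 and 1.18 rest on mixes found nowhere in the protocol and on one hazard shared by suppressed and viraemic starters. They vanish once baseline viral load is conditioned on. This stands, and it limits the ratio claim. Baseline viral load is not in the confounder list of section 4.2.4, but that list is not exhaustive, and sections 2.1.1 and 4.5.4 name pre-treatment viral load as a confounder.

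A reader might also infer that patients without a rule contaminate the case-control controls or risk sets. The documents do not support this. Sections 2.1.1 and 4.5.4 match on pre-treatment viral load and treatment status, with controls at risk when the case occurs. A profile that never yields a case is essentially not sampled, and controls for a case with baseline above 500 are already past month 6. Only the loss of cases remains.

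A reader might carry the 1.7-fold difference over to this study. It comes from another cohort with a median of 8 months' follow-up, and the protocol does not say whether events stayed at 669 after the exclusion. It shows that the choice of denominator matters, not how much it matters here.

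Finally, the 12-month proportion has no person-time denominator, and the person-time division is introduced among additional descriptive analyses. Both are true. But the proportion still cannot count patients without a rule, and the same paragraph calls incidence rates primary. Nor is this detail left to an analysis plan: the protocol states both the rules and the denominator, and they do not fit together.

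**Conclusion.** The point holds as a wrongly stated rule with a cheap remedy. Two conclusions need no assumption about how the groups differ:

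- Experienced patients above 500, and anyone detectable at or below 500, cannot be counted as failures in the rates or the 12-month proportions, and cannot become cases.
- For baseline above 500 the reported rate is roughly half the hazard after month 6, given complete 12-month follow-up and a constant hazard.

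The size of the dilution in the experienced stratum depends on the unknown share without a rule.

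The relative risk is a conditional matter. It is distorted if the groups differ in baseline viraemia or treatment status and the analysis does not condition on them; differing early stopping adds only a small effect in the calculations above. Differences are plausible, since sections 4.5.3 and 5 expect channelling. Stratifying by naive or experienced status helps, but the experienced stratum still mixes suppressed starters with viraemic ones who have no rule. The stronger reading, that the ratio reflects baseline mix rather than the drugs, is not supported: adjustment can remove most of that effect. Adjustment cannot correct the absolute rates or create events that no rule defines.

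**What to change.** 1. **Section 4.2.2:** state a failure rule for every baseline group. One option is to apply the rule of above 500 after 6 months to all patients with baseline above 500 whatever their prior treatment, and the two-consecutive rule to all at or below 500. Another complete set of rules would also serve.
2. **Section 4.5.3 and Synopsis:** for virologic failure, count person-time only from when the applicable rule can be met, which is month 6 for baseline above 500. Report exits before month 6 by treatment group, and keep the 12-month proportion from initiation alongside.
3. **Section 4.5.3:** stratify or adjust the failure comparison by baseline viral load (above 500, or at or below 500) as well as by naive or experienced status.

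The cost is protocol wording and a revised person-time derivation from viral loads and dates the cohorts already hold. Reported rates will be higher. Starting time at month 6 also conditions on remaining on the drug for six months, which can bias the comparison if early stopping differs between groups. That is why the early exits and the 12-month proportion must be shown with the rates. No change to case-control sampling is needed; a complete rule restores the missing cases.
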